## **6.8.           Unscheduled Visits**

Unscheduled procedures may occur at any time during the study. Vital Signs, ECOG, 12-lead ECG, bone scan and CT or MRI, may be conducted at these visits and recorded on the applicable eCRFs.

## **6.9.           Criteria for Discontinuation of Study Treatment**

See Section [3.4](#) for discontinuation criteria.

## **6.10.          Post Study Care**

If a subject has discontinued the study treatment due to toxicity, he/she should not have withdrawal of consent recorded as the reason for discontinuation. Instead, the reason for discontinuation must be recorded as due to adverse event.

Every attempt should be made to keep the subject in the study and continue collecting CT or MRI scans for tumor assessment at every 12 weeks until disease progression or initiation of systemic anti-tumor therapy other than treatment per protocol. If this is not possible or acceptable to the subject or investigator, the subject may be withdrawn from the study. The subject will be asked to attend the post-treatment follow-up assessment visit above when discontinuing from the study treatment.

## **6.11.          Replacement of Subjects**

If a subject is withdrawn from the study for any reason other than a DLT prior to completion of the DLT assessment window, a replacement subject will be enrolled at the same dose level as the replaced subject. To be evaluable for the DLT observation, a subject must receive at least 21 doses of GS-5829, complete all safety procedures through Day 28, or experience a DLT prior to Day 28.

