### **1.2.2.2. Nonclinical Toxicology**

Nonclinical safety pharmacology and toxicology studies have characterized the safety of GS-5829 through repeat dose toxicology studies. All pivotal toxicology studies were conducted in full compliance with Good Laboratory Practice regulations (21 CFR 58). The scope of the nonclinical safety evaluation is consistent with the guidance issued by the International Conference on Harmonisation (ICH).

In nonclinical pharmacology studies, GS-5829 showed no significant adverse effects on central nervous, respiratory or cardiovascular system functioning at the projected exposure and human target dose of 25 mg once daily.

The following target organs/systems were identified in the nonclinical toxicology studies: hematopoietic and male reproductive system (mice and dogs), the adrenal and skin (mice), and the gastrointestinal tract, respiratory and cardiac (dogs). With the exception of the adrenals in the mouse and the respiratory and cardiac hemorrhages observed in dogs, target organs are as expected based on the known pharmacology. The dog was the more sensitive species, with the no-observed-adverse-effect levels in the mouse and dog being 10 and 0.03 mg/kg/day respectively. The severely toxic dose in 10% of mice and the highest non-severely toxic dose (HNSTD) in dogs were 25 and 0.1 mg/kg/day, respectively.

Hematopoietic effects include decreases in white blood cells, lymphocytes, platelets and reticulocyte counts as well as mild reduced cellularity in the marrow in mice at doses of  $\geq 10$  mg/kg/day. Minimal to marked decrease in bone marrow cellularity, decrease in lymphocytes in the lymphoid tissues (spleen, thymus, lymph nodes and gastrointestinal associated lymphoid tissue), decrease in neutrophils and platelets were observed at 0.3 mg/kg/day in dogs. Elevated fibrinogen was also noted at 0.3 mg/kg/day in dogs.

Mild to moderate alveolar (lung) hemorrhage was observed at  $\geq 0.1$  mg/kg/day in dogs. Mild hemorrhage in the left atrioventricular valve of the heart was seen at 0.3 mg/kg/day in 1 of 6 dogs. The mechanism for the hemorrhage is not known. Prothrombin time and partial thromboplastin time measurements were normal. The anatomic pattern of the hemorrhage in the lung field and microscopy was considered potentially consistent with pneumonia, however bacteria were not identified.

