### **Dose Limiting Toxicity Definition**

A DLT is a toxicity defined below, considered possibly related to GS-5829, occurring during the DLT assessment window (Day 1 through Day 28) in each cohort:

- Grade  $\geq 4$  neutropenia (absolute neutrophil count [ANC]  $< 500/\text{mm}^3$ )
- Grade  $\geq 3$  neutropenia (ANC  $< 1000/\text{mm}^3$ ) with fever (a single temperature of  $> 38.3^\circ\text{C}$  or a sustained temperature of  $\geq 38^\circ\text{C}$  for more than one hour)
- Grade  $\geq 3$  thrombocytopenia
- Grade  $\geq 2$  bleeding (e.g. gastrointestinal, respiratory, epistaxis, purpura)
- Grade  $\geq 3$  or higher non-hematologic toxicity, except:
  - Grade 3 nausea or emesis with maximum duration of 48 hours on adequate medical therapy
  - Grade 3 diarrhea which persists for  $< 72$  hours in the absence of maximal medical therapy
- Grade  $\geq 2$  non-hematologic treatment-emergent adverse event (TEAE) that in the opinion of the investigator is of potential clinical significance such that further dose escalation would expose subjects to unacceptable risk
- Treatment interruption of  $\geq 7$  days due to unresolved toxicity

For certain toxicities, such as laboratory assessments without a clear clinical correlate, a discussion between the investigator and medical monitor may take place to determine if this adverse event (AE) should be assessed as a DLT necessitating dose reduction. However, any Grade 3 or Grade 4 elevation in AST or ALT associated with a Grade 2 elevation in bilirubin that is at least possibly related to study drug will be considered a DLT.

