### **3.5. Criteria for Removal from Study**

Subjects may be removed from the study for the following reasons:

- Documented progression of malignant disease
- Death
- Investigator discretion
- Non-compliance with study drug
- Subject never dosed with study drug
- Important protocol deviation
- Withdrawal of consent
- Lost to follow-up
- Study termination by the sponsor
- Intercurrent illness that would, in the judgment of the investigator, affect assessments of clinical status to a significant degree
- Unacceptable toxicity, as defined in the toxicity management section of the protocol, or toxicity that, in the judgment of the investigator, compromises the ability to continue study-specific procedures or is considered to not be in the subject's best interest

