### 5.3.1. Dose Adjustment of GS-5829

In the event of a Grade 3 or 4 hematologic or any non-hematologic toxicity that the investigator considers related to GS-5829 and is clinically significant, GS-5829 will be interrupted for a maximum of 28 days until the toxicity resolves to  $\leq$  Grade 1 or returns to baseline level.

Following resolution of the toxicity or the toxicity returns to baseline level, treatment may be restarted at a reduced dose as per [Table 5-1](#). If the toxicity does not resolve or return to baseline, study drug(s) GS-5829 and enzalutamide will be permanently discontinued and the subject will return for an End of Treatment and a 30 day Safety Follow-Up visit.

No dose reduction of GS-5829 below 1.0 mg is allowed.

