**8.2.1.3. DLT-Evaluable Analysis Set**

The DLT-Evaluable Analysis Set includes all subjects in the Safety Analysis Set who complete all treatment and safety procedures through Day 29, or experienced a DLT prior to Day 29. Determination of the MTD will be in DLT-Evaluable Analysis Set.

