3.1.4. Dose-Limiting Toxicity (DLT) Analysis Set

The DLT Analysis Set includes all subjects in the Safety Analysis Set who complete all or at least 21-day study treatment and have safety assessment through Day 28 of GS-5829, inclusive, or experienced a DLT prior to Day 28, exclusive. During the DLT assessment window, if a subject who fails to receive GS-5829 for at least 21 days for reasons other than DLT, another

subject will be enrolled at the same dose level for replacement. For subjects who are replaced but received at least 1 dose of study drug, they will be included in the Safety Analysis Set and not in the DLT Analysis Set.

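### A GS-5829-related toxicity that ends treatment in the DLT window but is not on the DLT list is not counted against the dose level (a narrow gap)

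*Protocol*

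**What the plan says.** Protocol 3.2 (and the synopsis) defines a DLT as a listed toxicity, possibly related to GS-5829, on Day 1 through Day 28. The only blood-count items are Grade 4 neutropenia, febrile Grade 3 neutropenia and Grade 3 or higher thrombocytopenia. The list also has Grade 2 or higher bleeding, Grade 3 or higher non-haematologic toxicity with short exceptions, Grade 2 or higher non-haematologic events that the investigator judges to make escalation unsafe, and an interruption of 7 or more "days due to unresolved toxicity". For laboratory findings without a clear clinical correlate, the investigator and medical monitor may discuss whether to call a DLT.

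Protocol 6.11 replaces subjects on this condition: "If a subject is withdrawn from the study for any reason other than a DLT prior to completion of the DLT assessment window". Protocol 3.5 lists among the reasons for study removal "Unacceptable toxicity, as defined in the toxicity management section of the protocol", and adds toxicity by investigator judgement.

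SAP 3.1.4 provides for replacement "if a subject who fails to receive GS-5829 for at least 21 days for reasons other than DLT", and leaves replaced subjects out of the DLT Analysis Set.

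Three sections define who is evaluable, each differently:
- Protocol 6.11: at least 21 doses, Day 28 safety procedures, or a DLT before Day 28, in a list that can be read as alternatives.
- Protocol 8.2.1.3: "complete all treatment and safety procedures through Day 29, or experienced a DLT prior to Day 29".
- SAP 3.1.4: at least 21 days of treatment with safety assessment through Day 28, or "experienced a DLT prior to Day 28, exclusive".

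**The concern.** In a 3+3 design, a subject who cannot stay on drug because of the drug carries information about tolerability. Here that information enters the formal count only if the event is on the list, and neither 6.11 nor SAP 3.1.4 makes an exception for related toxicity.

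The events left out are not far-fetched. Protocol 1.2.2.2 says of the mouse data: "Hematopoietic effects include decreases in white blood cells, lymphocytes, platelets and reticulocyte counts". It also reports reduced marrow cellularity in dogs. Yet anaemia and lymphopenia of any grade, and afebrile Grade 3 neutropenia, are not listed, and the investigator-judgement item covers non-haematologic events only.

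At stake is the formal tally. The next cohort opens on DLT counts (3.2), DLT incidence is the phase 1b primary endpoint (8.1.2), and the MTD is determined in the DLT-evaluable set (8.2.1.3). Leaving such subjects uncounted tilts that tally toward clearing a level.

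**Working it through.** The plan states no figure for this point, so the check is a reading of the rules followed by an illustration.

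**1. What the list already catches.** Under 5.3.1, for related, clinically significant Grade 3-4 haematologic toxicity, "GS-5829 will be interrupted for a maximum of 28 days until the toxicity resolves to" Grade 1 or less, or baseline. A single toxicity hold of 7 days or more for an unresolved event is a DLT. Fewer than 21 of 28 doses means at least 8 missed, so one continuous hold of that length already meets the interruption item. Most dosing shortfalls from toxicity are caught.

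**2. What escapes: late removal.** Suppose related Grade 4 anaemia is found at the Day 22 visit and the subject is removed from the study on Day 23 after 22 doses.
- Anaemia is not listed.
- Days 23 to 28 are 6 days, so a 7-day interruption cannot fit inside the window.
- 6.11 replaces the subject.
- Without safety assessment through Day 28, the subject also fails the first limb of SAP 3.1.4.

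An earlier permanent stop escapes if it is not read as an interruption, or if the toxicity resolves within 7 days. The protocol does not settle that reading. Table 5-2 requires permanent discontinuation for GS-5829-related Grade 4 toxicity in combination treatment. The table is titled for Group 2, so applying it to phase 1b combination cohorts is an inference.

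**3. A less likely route: split holds.** Holds on Days 8-11 and 22-25 leave 28 - 4 - 4 = 20 doses, below 21, with neither hold reaching 7 days. This needs two recoveries to Grade 1 or baseline within 4 days each. With reassessment only at scheduled visits, a hold from Day 8 to the Day 15 visit already lasts 7 days.

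**4. Effect of one subject, with no assumed rate.** Assume no DLT in the replacement.

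| Situation | Replaced | Counted as a DLT |
|---|---|---|
| First three subjects, no other DLT | 0/3, next level opens | 1/3, expand to 6 |
| Six subjects, one other DLT | 1/6, cleared | 2/6, not cleared |

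**5. Illustration of frequency.** All rates are assumptions. Let d be the rate of other listed DLTs, w the rate of related-toxicity stops or shortfalls, and c the share of w that is already a DLT. With q = 1 - p, a level clears (3 then 6 subjects) with probability q³ + 3pq⁵, where:
- replaced: p = (d + cw) / (1 - (1 - c)w)
- kept as a non-event: p = d + cw
- counted: p = d + w

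For d = 0.20 and w = 0.15, counting every stop gives p = 0.35 and a clearing probability of 0.396. Against that:

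| c | Replaced: p, P(clear) | Kept as non-event: p, P(clear) | Replaced minus counted |
|---|---|---|---|
| 0.8 | 0.32/0.97 = 0.330, 0.435 | 0.320, 0.454 | 3.8 points |
| 0.9 | 0.335/0.985 = 0.340, 0.415 | 0.335, 0.425 | 1.9 points |

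Starting with 4 subjects (q⁴ + 4pq⁵) gives 0.380 and 0.360 against 0.341.

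Over d = 0.10-0.25, w = 0.05-0.15 and c = 0.8-0.9, the rise runs from 0.7 points (d = 0.25, w = 0.05, c = 0.9: 0.5015 against 0.4943) to 5.0 points (d = 0.10, w = 0.15, c = 0.8: 0.650 against 0.600). These inputs put the uncaught rate (1 - c)w between 0.1 × 0.05 = 0.5% and 0.2 × 0.15 = 3% of subjects. If it were 5-10%, with listed-DLT rates of 10-30%, the same comparison gives about 7 to 18 points. At zero there is no difference.

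**6. Where the effect comes from.** Keeping the subject as a non-event raises the clearing probability slightly more than replacement does (0.454 against 0.435; 0.425 against 0.415). The driver is the DLT definition, not replacement.

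**The case against.** The best case against has five parts.

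- **The laboratory clause.** A reader might infer that the events in question could not be DLTs on any reading. The documents do not support that: the discussion clause in 3.2 may reach isolated blood-count findings, and a cumulative reading of the 7-day item would catch the split holds. The clause is discretionary, however. It is limited to findings without a clear clinical correlate, so it may not reach symptomatic anaemia.
- **Replacement is the milder handling.** A reader might infer that 6.11 is itself what inflates escalation. Step 6 shows otherwise. Adding an exception to 6.11 alone would not close the gap.
- **The SAP came too late to affect dosing.** A reader might infer that SAP 3.1.4 let levels open. SAP section 1 says all phase 1b subjects had already stopped study drug, so 3.1.4 governs only the reported DLT set. Protocol 6.11 requires withdrawal from the study, and 6.10 asks sites to make every attempt to keep toxicity discontinuations in it.
- **Other safeguards.** The Safety Review Team reviews safety and tolerability (3.2). Combination escalation may stop early on tolerability, and the expansion dose may be below the MTD. SAP 7.1.6.1 tabulates events leading to discontinuation, interruption and reduction in the Safety Analysis Set. SAP 3.1 lists reasons for exclusion by subject. SAP 7.1.7.1 plans only a listing of DLT events, with no per-level rate for exclusion to bias.
- **Human data.** Protocol 1.5 reports no discontinuations for adverse events in the first-in-human study, and 1.2.3 no dose-related laboratory trend. These are early, low-dose data, and the DLTs reported there are of kinds that the list covers.

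All of this limits the point, but none of it removes it. The written rule for opening a cohort and naming the MTD is still the DLT count, and a related-toxicity stop is still not in it.

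**Conclusion.** The point holds in narrow form and is minor. A permanent stop or study removal for GS-5829-related toxicity does not count unless the event is itself listed or is called a DLT by discretion. The residual class is mainly unlisted haematologic toxicity handled as a stop rather than as an interruption of 7 days or more.

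That one subject can change a cohort's result follows from the rules alone. The 0.7 to 5.0 points rest entirely on assumed rates. The documents do not show that any such subject occurred, so nothing here supports saying that a level was wrongly cleared or that the MTD is too high. The effect is on the formal DLT and MTD tally, not on every safety decision.

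The differing evaluability definitions are a consistency fault with little effect of their own. For example, a Day 28 DLT in a subject with 21 days of treatment and a Day 28 assessment still enters the SAP set through its first limb.

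**What to change.** - **Protocol 3.2 and synopsis:** add as a DLT permanent discontinuation, or fewer than 21 of 28 doses, because of GS-5829-related toxicity on Days 1-28.
- **Protocol 6.11, 8.2.1.3 and SAP 3.1.4:** allow replacement or exclusion only when the stop or shortfall is not due to GS-5829-related toxicity. Use one definition of evaluable: (at least 21 of 28 doses and safety procedures through Day 28) or a DLT on Days 1-28 inclusive.
- **SAP, for the report:** keep any such subjects in the DLT set and give the per-level tally with and without counting them as events. With phase 1b dosing over, this is the part that can still affect this study; the protocol wording would serve later escalations.

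The cost is one list item and one clause in each of three sections. No new data are needed: dosing, relatedness and discontinuation reasons are collected, and 6.10 already requires toxicity stops to be recorded as adverse events. The downside is that escalation may be slightly slower.

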Enzalutamide is a strong CYP3A4 inducer, which has been demonstrated to decrease the AUC of a CYP3A4 substrate (midazolam) by 86%; therefore further dose escalation of the combination therapy will be performed in these subjects prior to initiation Phase 2 Dose Expansion. As the concern is for decreased GS-5829 exposure, the initial dose level of the combination therapy will be 160 mg of enzalutamide combined with a starting dose of GS-5829 that has been determined to be safe and tolerable in the single agent dose escalation. Enzalutamide dosing will begin approximately 2 weeks prior to GS-5829 dosing to achieve near maximal CYP3A4 induction to reduce changes in GS-5829 exposure over the first cycle. PK evaluations will be performed and if indicated and supported by PK, safety and tolerability, additional cohorts with higher doses and/or more frequent dosing (ie, twice daily) of GS-5829 in combination with enzalutamide may be tested. The total daily dose will not increase by more than 100% in the next cohort.

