**Table 5-1. Dose Reduction of GS-5829**

Dose at time of toxicity (mg)	Restarting dose level (mg)
6	5
5	4
4	3
3	2
2	1.0

If a subject develops a recurrence of the same Grade 3 or 4 hematologic or any non-hematologic toxicity that the investigator considers related to GS-5829 and is clinically significant at the lower dose, then the subject should be permanently discontinued from all study drug(s).

After the 28 day DLT period in the Dose Escalation Phase and at any time in the Dose Expansion Phase, in the event of a Grade 2 hematologic or non-hematologic toxicity the investigator considers related to GS-5829, GS-5829 may be interrupted per the investigator's discretion for a maximum of 28 days and resumed at either the same or a lower dose per [Table 5-1](#).

Subjects who dose interrupt for a non-drug related toxicity for up to 28 days, and are deemed by the investigator to be clinically benefiting from GS-5829 prior to dose interruption, may resume GS-5829 treatment. Non-drug related dose interruptions for longer than 28 days in subjects who do not have disease progression may be considered for resumption of GS-5829 after discussion with the Medical Monitor.

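### Three conflicting DLT-evaluability rules, none tied to the assigned dose, let a subject reduced early in the window count as DLT-free at a level he mostly did not take

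*Protocol*

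**What the plan says.** Evaluability is defined in three places.

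- **Protocol 6.11 (Replacement of Subjects):** "To be evaluable for the DLT observation, a subject must receive at least 21 doses of GS-5829", complete all safety procedures through Day 28, or have a DLT before Day 28. The list is joined by 'or', so the dose count is not clearly mandatory. No dose level is named.
- **Protocol 8.2.1.3 (DLT-Evaluable Analysis Set):** completion of all treatment and safety procedures through Day 29, or a DLT before Day 29. This is the set named for determining the MTD.
- **SAP 3.1.4 (DLT Analysis Set):** all or at least 21 days of study treatment with safety assessment through Day 28, or a DLT before Day 28. The SAP replaces "a subject who fails to receive GS-5829 for at least 21 days for reasons other than DLT" and leaves that subject out of the DLT set.

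The dose-modification text is in protocol 5.3.1. "In the event of a Grade 3 or 4 hematologic or any non-hematologic toxicity that the investigator considers related to GS-5829" and that is clinically significant, GS-5829 is interrupted until recovery to Grade 1 or baseline, after which "treatment may be restarted at a reduced dose as per" Table 5-1. This paragraph carries no time limit. A later paragraph on Grade 2 toxicity does: it applies "After the 28 day DLT period in the Dose Escalation Phase and at any time in the Dose Expansion Phase".

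The DLT definition in protocol 3.2 covers listed toxicities "occurring during the DLT assessment window (Day 1 through Day 28) in each cohort". A treatment interruption of 7 days or more for unresolved toxicity is on the list. A dose reduction is not. Under SAP 3.2, actual treatment differs from assigned treatment only if it differed for the entire treatment duration, so a reduction part-way through the window does not move the subject to a lower level.

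**The concern.** A 3+3 decision rests on the number of DLTs among 3 to 6 subjects who are each taken to have tested the assigned dose for 28 days. A subject who spends much of the window on a lower dose has not done that. If he counts as DLT-free at the higher level, a toxicity that continued full dosing might have produced cannot appear, and the level looks safer than it is. No passage says how a subject reduced within Days 1-28 is to be classified.

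The phase 1b primary endpoint (DLT incidence) and the MTD objective depend on this classification. With cohorts this small, one subject can change the escalation decision. Because the three definitions also differ, two analysts could report different denominators for the same level.

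**Working it through.** **1. Which triggers are not already DLTs.** Grade 4 neutropenia, febrile Grade 3 neutropenia, Grade 3 or higher thrombocytopenia, Grade 2 or higher bleeding and most Grade 3 or higher non-hematologic events are DLTs. Afebrile Grade 3 neutropenia and Grade 3-4 anemia are not on the list, yet fall under the 5.3.1 hematologic trigger when related and clinically significant. For the combination, Table 5-2 requires permanent discontinuation for Grade 4 toxicity related to GS-5829, so there the route is through Grade 3 only.

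**2. Dose count over the window.** Inputs: 28 days, once-daily dosing (28 planned doses), the 21-dose threshold, and 7 days as the hold that is itself a DLT. Let d be full doses and g the hold in days. Reduced doses = 28 - d - g; total = 28 - g.

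- The longest hold that is not a DLT is 6 days: 28 - 6 = 22 doses, still at least 21. A single hold short of a DLT therefore never breaks the dose count unless other doses are missed.
- Most doses are reduced when 28 - d - g > d. With a hold of 0-1 day this needs d of at most 13; with a 6-day hold, at most 10. Onset must therefore fall before about Day 14.
- Example: dosed Days 1-8, held Days 9-12, restarted lower on Day 13. Full doses 8; reduced 28 - 8 - 4 = 16; total 24. Reduced share 16/24 = 67% of doses and 16/28 = 57% of days.
- The first step in Table 5-1 is a cut of 1/6 = 17% (6 to 5 mg), rising to 1/2 = 50% (2 to 1 mg).

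**3. How the example is classified.**

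| Rule | Result for 8 full + 16 reduced doses, no DLT |
|---|---|
| Protocol 6.11 | Evaluable: 24 is at least 21 |
| SAP 3.1.4 | In the set: at least 21 days, if assessed through Day 28 |
| Protocol 8.2.1.3 | Unclear: out if 'all treatment' means every planned dose, in if it means treatment as modified |

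**4. Illustration of size.** The plan gives no figure to reproduce. With 3 subjects expanded to 6 after one DLT, and q = 1 - p, the chance of clearing a level is q^3 + 3pq^2 × q^3.

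- True rate p = 1/3: 0.296 + 0.132 = 0.428.
- Assumption A: 10% to 30% of subjects are reduced early and their DLT risk is halved. The observed rate is 1/3 × 0.95 = 0.317 to 1/3 × 0.85 = 0.283; the chance of clearing is 0.461 to 0.529. (Rounding p to 0.33 gives 0.434, rising to 0.467-0.535.)
- Assumption B: 10% to 25% of DLTs are hidden. The observed rate is 0.30 to 0.25; the chance is 0.494 to 0.600.

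Together: 43% rising to about 46-60%. The 10-30%, the halving and the 10-25% are assumptions with no basis in the documents.

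**The case against.** The strongest reply is that the route is narrow. The trigger must not be a DLT, recovery to Grade 1 or baseline must come in under 7 days, and onset must be early. That stands, and it is why the claim is that such a subject *can* count as DLT-free, not that reduced subjects in general do.

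A second reply is that protocol 8.2.1.3, not the 21-dose rule, governs the MTD. That also stands, but it does not close the gap. Read loosely, it admits the reduced subject. Read strictly, it drops anyone with a toxicity hold short of a DLT, which removes poorly tolerated courses from the denominator.

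A third is that nothing is hidden. Replaced subjects stay in the Safety Analysis Set, reasons for exclusion are listed (SAP 3.1), adverse events leading to interruption or reduction of GS-5829 are tabulated (SAP 7.1.6.1), protocol 8.6.1 reports the number and timing of dose modifications, and the Safety Review Team looks at tolerability. This is fair. But none of these outputs is tied to DLT status within the 28-day window, and SAP 7.1.7.1 plans only a listing of DLT events.

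A reader might infer several stronger points that the documents do not support.

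- *That Grade 2 non-hematologic events open the same route.* The words 'any non-hematologic' in 5.3.1 can be read that way, but the time limit in the Grade 2 paragraph would then do little. The hematologic examples do not depend on this reading.
- *That two 4-day holds (28 - 8 = 20 doses) remove a subject who could not tolerate the dose.* The DLT item does not say the 7 days must be consecutive, recurrence of the same toxicity at the lower dose leads to discontinuation, and replacement in 6.11 is worded for subjects withdrawn from the study.
- *That 21 doses could mean 10.5 days (21/2) under twice-daily dosing.* Such cohorts are only a possibility in protocol 1.3.1, SAP 1.2 describes once-daily dosing, and SAP 3.1.4 already counts days.
- *That the phase 2 dose would be too high.* SAP section 1 states that the study stopped during escalation, before phase 2.

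**Conclusion.** The gap is real. Three evaluability rules conflict, none ties exposure to the assigned dose, and following protocol 6.11 or SAP 3.1.4 as written can credit a DLT-free result to a dose the subject mostly did not take. The direction is clear: at the affected level the DLT rate can be biased down and the MTD up. It does not follow that the MTD is in fact biased, because the documents do not show that any subject took this course. The rise from 43% to about 46-60% illustrates sensitivity under the stated assumptions and does not estimate the effect.

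The point is worth correcting but is not critical. Its effect is confined to the phase 1b DLT and MTD results.

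**What to change.** Reconcile protocol 5.3.1, 5.3.2 with Table 5-2, 6.11 and 8.2.1.3 with SAP 3.1.4, so that there is one evaluability definition and one end day. State it in days of GS-5829 at the assigned dose level and schedule, with safety assessments complete, or a DLT. A subject reduced in the window without a DLT is then not counted as DLT-free at that level. Protocol 8.2.1.3 must be included, since it is the set named for the MTD.

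That change alone would make reduced subjects non-evaluable and could itself remove tolerability problems from the denominator. So pair it with reporting. For each dose level, give the Safety Review Team and the clinical study report the number of subjects reduced, under-dosed or replaced for GS-5829-related toxicity within the window. Show DLT n/N twice: once under the definition, once with those subjects counted as events.

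The cost is about a sentence in each place, one extra table from dosing data already collected, and a less favourable second count. While escalation is enrolling, it also costs an occasional replacement subject, which the plan already allows. SAP section 1 says all phase 1b subjects have stopped study drug, so for the final analysis the cost is instead a smaller evaluable N at some levels, which should be shown. This changes classification and reporting only; no dosing or dose-modification rule is proposed.
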